Appendix K: Six-Month Follow-Up Survey

Phone Contact:

Hello, my name is _____, I'm calling from the (Name of VAMC). I am trying to reach [Name of Veteran].

Not Present: I'll call back another time, thank you. Is there a good time to try calling back?

Voicemail: Hello, my name is [name of research team member], I am calling from the (Name of VAMC). I wanted to speak with [Name of Veteran] about the Resource Needs Study. It's time to complete one of the brief questionnaires that are part of this study, it will only take about 10 minutes to complete. Please contact me at [name]. If you get my voicemail please leave your name, the best number to reach you at, and the most convenient times to reach you. Thank you.

Present: Hello, my names is [name of research team member] and I work at the (Name of VAMC). I wanted to speak with you about the Resource Needs Study you are participating in. It's time to complete one of the brief questionnaires that are part of this study, it will only take about 10 minutes to complete. Do you have a few minutes now?

If No: When is a good time for you to answer some questions about your social circumstances? (*SCHEDULE A TIME AND CONFIRM BEST CONTACT NUMBER*)

If Yes: Great, let's get started.

Screening Survey

HOUSING AND UTILITIES

1. In the past 6 months, have you been living in stable housing that you own, rent, or stay in as part of a household?

- Yes
- No

2. Are you worried or concerned that in the next 2 months you may NOT have stable housing that you own, rent, or stay in as part of a household?

- Yes
- No

3. In the past 6 months has the electric, gas, oil or water company threatened to shut off service in your home?

- Yes
- No
- Already shut off
- Not applicable

EMPLOYMENT AND FOOD

4. Are you currently:

- Employed for wages
- Self-employed
- Out of work for 1 year or more
- Out of work for less than 1 year
- A Homemaker
- A Student
- Retired
- Unable to work

5. How often were the following statements true for you in the past 6 months?

i. Within the past 6 months, you worried that your food would run out before you got money to buy more.

- Often true
- Sometimes true
- Never true

ii. Within the past 6 months, the food you bought just didn't last and you didn't have money to get more.

- Often true
- Sometimes true
- Never true

LEGAL AND TRANSPORTATION

6. Are you currently dealing with any legal issues, for which you may need assistance?

- Yes
- No

7. In the past 6 months, has lack of transportation kept you from medical appointments, meetings, work, or getting things needed for daily living: Check all that apply

- Yes, it has kept me from medical appointments or from getting my medications
- Yes, it has kept me from non-medical meetings, appointments, or getting the things that I need
- No

SOCIAL AND EMOTIONAL STATUS

8. In the last 6 months, how often did you feel lonely or isolated?

- Never
- Rarely
- Sometimes
- Often
- Always

9. Stress is when someone feels tense, nervous, anxious, or can't sleep at night because their mind is troubled. In the last 6 months, how often did you feel stressed?

- Not at all
- A little bit
- Somewhat
- Quite a bit
- Very much

EXPOSURE TO VIOLENCE

10. Is anyone in your life hurting or threatening you?

- Yes
- No

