5.5 Study Evaluations

RCT participants will be asked to complete three brief surveys over a 6-month period. A small sub-set of participants will additionally be invited to participate in qualitative interviews.

Index Unmet Need Screen (survey #1): We will assess unmet needs among trial participants based on the index screen (administered prior to randomization). See **Appendix I** for the Index Unmet Need Survey.

Eight-Week Follow-Up Survey (survey #2): Eight weeks after the index screen, the RA will conduct phone follow-up with each Veteran to assess if they connected to any new resources in the intervening time and if so, to which one(s). See **Appendix J** for the Eight-Week Follow-Up Survey and accompanying phone script.

6-Month Unmet Need Re-Screen (survey #3): Six months after the index screen and by phone, the RA will re-administer the unmet need survey modified slightly

to exclude questions related to preferences for assistance (see **Appendix K** for the Six-Month Unmet Need Survey and accompanying phone script). We will define unmet need reduction in two ways: 1) one or more of baseline unmet needs no longer identified as an unmet need at the 6-month re-screen; and 2) percentage of baseline needs not reported as unmet needs at 6-month rescreen.

Qualitative Interviews with Veterans: Among study participants, we will purposefully select and recruit 60 Veterans to participate in qualitative interviews. The interviews are designed to understand the conditions that facilitate or impede a Veteran connecting to resources, as well as the conditions under which resources do or do not address a Veteran's needs. The RA at each study site will conduct the interviews. See **Appendix L and M** for the Veteran Interview Guides and accompanying phone scripts).

Qualitative Interviews with Representatives of VA and Community Resources: To understand how VA- and community-based programs experience the intervention, we will interview a purposeful sample of the VA- and community-based programs that trial participants used as a result of the intervention. The RA at each study site will conduct the interviews. See **Appendix N** for the Resource Representative Interview Guide and accompanying phone script.

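### The 6-month re-screen asks six of nine needs over a window that opens at the index screen, so a need resolved during follow-up (clearest for food) can count as not reduced

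*Combined protocol and SAP*

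**What the plan says.** Section 5.5 sets the timing: "Six months after the index screen and by phone, the RA will re-administer the unmet need survey". It gives two definitions of reduction: "one or more of baseline unmet needs no longer identified as an unmet need at the 6-month re-screen", and "percentage of baseline needs not reported as unmet needs at 6-month rescreen". No call window is stated.

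Appendix K uses two kinds of recall period.

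- **Six-month look-back (six needs):** housing item 1, "In the past 6 months, have you been living in stable housing that you own, rent, or stay in as part of a household"; utilities, "In the past 6 months has the electric, gas, oil or water company threatened to shut off service in your home"; food, "Within the past 6 months, you worried that your food would run out before you got money to buy more"; transportation, "In the past 6 months, has lack of transportation kept you from medical appointments, meetings, work, or getting things needed for daily living"; and isolation and stress, both over the last six months.
- **Present tense (three needs):** job status; legal, "Are you currently dealing with any legal issues, for which you may need assistance"; and safety.

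Housing also has item 2, on worry about the coming two months. The index screen (Appendix I) uses the same six-month look-back for the same six needs. Its follow-up branch for food opens on 'Often' or 'Sometimes' true.

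Appendix A has Resource Sheets mailed within two days of index. The social worker makes contact within two business days, follows up a week after the action plan, then calls every two weeks for up to seven weeks.

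Section 5.6 plans the need-reduction analysis on N=220, with 80% power at OR 2.94 and an ICC of .01. It also uses need reduction in the exploratory mediation analysis.

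**The concern.** Both definitions ask whether a baseline need has gone by the re-screen. For six needs, the item instead asks whether the need was present at any time, or how often, since about the index screen. The intervention starts within days of index and cannot resolve most needs at once, so a success may be preceded by some weeks of need inside the recall window. A Veteran who reports those weeks truthfully is scored as not reduced.

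If this is common, a null or altered need-reduction result could partly reflect the wording of the look-back. The mediation path from connection to need reduction would be blurred in the same way. The available text contains no current-status question for these six needs, and no rule that scores a need resolved within the window as reduced.

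**Working it through.** **1. Window.** An on-time call covers month 0 to month 6 after index. A call k days late moves the opening to k days after index. On an any-occurrence item, a need scores as cleared only if it ended before the window opened. Example: a food need ending at week 8 has been absent for 26 − 8 = 18 weeks, yet 'Sometimes true' remains a truthful answer.

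**2. Item by item (Appendix K).**

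| Need | Item | Exposure to the problem |
|---|---|---|
| Food | 5 | Clear, if 'Sometimes true' scores as a need (inferred from the Appendix I branch) |
| Housing | 1 | Possible but ambiguous: a Veteran housed midway could answer Yes or No |
| Utilities, transportation | 3, 7 | Only if a new event occurs after index |
| Isolation, stress | 8, 9 | Weaker: graded scales can fall below threshold |
| Job status, legal, safety | 4, 6, 10 | None: asked as current |

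**3. The plan's own figure.** 880 × 0.5 × 0.5 = 220. d = ln(2.94) × √3/π = 0.595, so f² = d²/4 = 0.088, which rounds to .09. Design effect = 1 + (220/3 − 1) × 0.01 = 1.723. Effective N = 220/1.723 = 127.7, or about 42.6 per arm. Two-arm power at d = 0.595 is 0.783, close to the stated 80%.

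**4. Illustration of size.** The baseline rate, the carry-over share r (resolved needs still reported) and the number of needs per Veteran are not in the documents. Assume 30% of needs truly resolved in one arm. With OR 2.94 the odds in the other are 2.94 × 0.30/0.70 = 1.26, giving t = 55.8%. Unresolved needs are assumed always reported. The observed share is q = t(1 − r). With n = 42.6, two-sided 0.05,

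power = Φ{[|q₁ − q₀| − 1.96√(2q̄(1 − q̄)/n)] / √([q₀(1 − q₀) + q₁(1 − q₁)]/n)}.

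One look-back need, equal carry-over:

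| r | Observed | Difference (points) | Power, n = 42.6 | Power, n = 73 (no design effect) |
|---|---|---|---|---|
| 0% | 30.0% vs 55.8% | 25.8 | 68% | 89% |
| 25% | 22.5% vs 41.8% | 19.3 | 48% | 71% |
| 50% | 15.0% vs 27.9% | 12.9 | 30% | 47% |
| 75% | 7.5% vs 13.9% | 6.4 | 16% | 24% |

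The 68% starting point is below the 78% of step 3 because this is a binary comparison, not the standardised-mean conversion.

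**5. Several needs.** For definition 1 with m independent look-back needs, the observed share is 1 − (1 − q)^m.

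- *Three needs:* differences at the four values of r are 25.6, 26.8, 23.9 and 15.4 points; power at n = 42.6 is 83%, 76%, 60% and 35%.
- *Four needs:* the difference goes from 20.2 (r = 0) to 24.6 (25%) and 25.1 (50%), so it widens.
- *Two look-back needs and one current need,* share 1 − (1 − q)²(1 − t): power is 83%, 80%, 76% and 72%.

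For definition 2 the differences are those of the one-need table, whatever m is.

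**6. Unequal carry-over, one need.** With r = 50% in Screening and 25% in Assistance, 15.0% vs 41.8% is observed (26.8 points). Reversed, it is 22.5% vs 27.9% (5.4 points).

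**7. Error in the other direction.** Suppose a share e of needs counted at index had already ended and do not recur. Observed within-arm reduction is e + (1 − e)t(1 − r). With t = 0.30 and r = 0.50, this equals 0.30 when e = 0.15/0.85 = 0.18. Below that share reduction is understated; above it, overstated.

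**The case against.** The strongest defence is that index and re-screen use matched six-month windows. That is a legitimate like-for-like measure of change, and a reason to keep every item and both definitions. It does not remove the misclassification of a need resolved inside the second window.

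Three stronger readings are tempting, and the documents do not support them.

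- *Reduction is understated in every arm.* A need that ended before index still counts at baseline and can later score as reduced without help. The net direction within an arm is unknown (step 7).
- *The arm difference always shrinks.* Equal carry-over shrinks it for one look-back need and for the percentage definition. For definition 1 with several needs the absolute difference can widen (step 5). With unequal carry-over the direction is not assured.
- *All six look-back needs are equally affected.* Only food is clear, and even that rests on a threshold inferred from Appendix I, since Appendix K states no scoring rule. Housing scoring is itself unsettled: the Appendix I branch opens on a Yes to stable housing, and item 2 of Appendix K captures only worry about the next two months.

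The eight-week survey asks whether the Veteran got the help wanted. It does so only among those who connected, and well before the re-screen, so it is a partial check at most.

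**Conclusion.** The point stands as a measurement weakness in a secondary outcome and in the exploratory mediation that uses it. The primary outcome, connection at eight weeks, is untouched. A need that persisted after index and was then resolved can be truthfully reported and scored as not reduced under both definitions. This is clear for food and less certain for the other five look-back needs.

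The size is not derivable from the documents. Under the stated assumptions, power for a single look-back need could fall from about 68% to between 48% and 16%. In the mixed three-need case it falls only from 83% to 72%. These figures rest on an assumed 30% resolution rate, assumed carry-over, independence between needs and the plan's ICC of .01. The change is worth making because it is cheap, not because serious harm has been shown.

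**What to change.** Keep all Appendix K items and both definitions in section 5.5. After a positive food answer, add 'Is this still a problem now?'. Preferably add it after positive answers on the other five look-back needs too. Report a current-status version of need reduction as a supplementary comparison between arms. The percentage definition is the more informative for this version, because definition 1 can approach a ceiling (66% vs 91% with three needs and no carry-over in step 5).

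State two limits with it. The answer is self-reported to a research assistant who may know the arm, since Appendix A has that role open the envelope and section 5.5 has it make the six-month call. There is also no matching index item, so the new version does not measure within-arm change.

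For re-screens already completed, state the limitation and report legal and safety needs, which are asked as current, separately. Do not use job status for this: the index question on wanting help with work (Appendix I, 9a) is not repeated in Appendix K, and status alone does not show a need.

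The cost is a survey amendment, up to six short conditional questions in a call of about 10 minutes, and no current-status data for earlier re-screens. The supplementary version would therefore rest on fewer than the planned 220 if any re-screens precede the amendment.

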Secondary data may also be stored and analyzed on the VA Boston HCS server behind the firewall. Access to the computer systems is restricted and password protected. All research computers are located in locked offices and computers are password protected. Access to CHOIR offices is restricted. All space accessible to the public is separated from research offices.

For all secondary data, we will take all necessary steps to protect privacy and confidentiality, in accordance with VA regulations and other applicable laws. All information on individuals will be kept confidential. Consistent with HIPAA regulations, we will use scrambled identifiers (when available) to allow linkages across files while protecting an individual's identity or we will de-identify the datasets. Only project personnel will have access to the data.

Quantitative Data (Surveys): We will construct a secure, password protected database in VA REDCap (to which we already have access as a team) to input the survey data. Survey data will be stored in this secure database at VA Boston and all personnel who need access will be able to connect to the server. Data will be cleaned and checked for accuracy by the project manager and data analyst. Mishandling of research data would compromise participant confidentiality. Thus, all possible measures will be taken to assure Veteran confidentiality. In addition, we will construct a secure, password protected database to create a record of study participants and those who have opted out of the study, using scrambled SSNs. This will be stored on a secure VA Boston server.

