Appendix I: Index Unmet Needs Screening Tool

DEMOGRAPHICS

1. Please indicate which of following types of people currently live with you in your household (*check all that apply*)

- My spouse or partner
- My child(ren) under age 18
- My adult child(ren) age 18 or older
- My parent(s)
- Extended family
- Roommate(s) not related to me
- Other individuals

2. Overall, which one of the following best describes how well you are managing financially these days?

- Living comfortably
- Doing OK
- Just getting by
- Finding it difficult to get by

3. Are you of Hispanic or Latino origin or descent?

- Yes, Hispanic or Latino
- No, not Hispanic or Latino

4. What is your race? Please select all that apply.

- White
- Black or African-American
- Asian
- Native Hawaiian or other Pacific Islander
- American Indian or Alaska Native
- Other

5. What is your gender

- Man
- Woman
- Transgender man
- Transgender woman
- Non-binary
- Other

HOUSING AND UTILITIES

6. In the past 6 months, have you been living in stable housing that you own, rent, or stay in as part of a household?

- Yes
- No

7. Are you worried or concerned that in the next 2 months you may NOT have stable housing that you own, rent, or stay in as part of a household?

- Yes
- No

7a. (If Yes to Q6 or Q7): Are you already receiving assistance with your housing needs?

7b. (If Yes to 7a): Would you like additional assistance?

7c. (If No to 7a): Would you like assistance with your housing needs?

8. In the past 6 months has the electric, gas, oil or water company threatened to shut off service in your home?

- Yes
- No
- Already shut off
- Not applicable

8a. (If Yes/Already shut off): Are you already receiving assistance with your gas, oil or water company needs?

8b. (If Yes to 8a): Would you like additional assistance?

8c. (If No to 8a): Would you like assistance with your gas, oil or water company needs?

EMPLOYMENT AND FOOD

9. Are you currently:

- Employed for wages
- Self-employed
- Out of work for 1 year or more
- Out of work for less than 1 year
- A Homemaker
- A Student
- Retired
- Unable to work

9a. Do you want help finding or keeping work or a job (check all that apply)?

- Yes, help finding a job
- Yes, help keeping work
- I do not want or need help
- I am already receiving assistance with my employment needs

10. How often were the following statements true for you in the past 6 months?

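### The six-month call asks whether anyone is hurting the Veteran without checking that the Veteran can talk privately, and a guarded No can be scored as a reduced need

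*Combined protocol and SAP*

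**What the plan says.** Section 5.5 sets the mode of the re-screen: "Six months after the index screen and by phone, the RA will re-administer the unmet need survey modified slightly". It defines unmet need reduction in two ways: "one or more of baseline unmet needs no longer identified as an unmet need at the 6-month re-screen" and "percentage of baseline needs not reported as unmet needs at 6-month rescreen".

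The Appendix K script is available from greeting to last item. Once the Veteran is on the line, the caller names the study and asks "Do you have a few minutes now". A No leads to a branch that schedules another time and confirms the contact number. A Yes leads straight into housing, utilities, employment, food, legal issues, transportation, loneliness and stress, ending with item 10: "Is anyone in your life hurting or threatening you". Yes and No are the only printed responses.

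The voicemail text says "I wanted to speak with [Name of Veteran] about the Resource Needs Study". The branch for someone else answering gives only the caller's name, the medical center and the Veteran's name. Appendix J uses the same voicemail wording and the same time check, and its first question reads back the needs the Veteran identified at the index screen.

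**The concern.** Section 5.1 (Risk to Subjects) names loss of confidentiality as the main risk of the study. Followed as written, the six-month script has the research assistant ask about being hurt or threatened without knowing who is within hearing. The index screen expects shared households: its first household option is "My spouse or partner".

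Two things are at stake. The first is protection of a Veteran who is overheard answering. Declining is not a full safeguard, because a refusal at that item can itself be telling. The second is the validity of the answer. A Veteran who disclosed the need at the index screen and cannot speak freely six months later may say No. The form then has nothing to separate that No from a need that has gone away.

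**Working it through.** **The text.** No figure in the plan is in dispute, so the first step is to set the provisions side by side.

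- *Appendix K, before the questions:* time only. Nothing asks about being alone, being on speaker or being able to talk.
- *Appendix K, item 10:* Yes or No, with no code for declined or not asked.
- *Section 5.1, survey data protections:* REDCap storage, passwords and access.
- *Section 5.1, Veterans who become upset:* staff training, a reminder of the right to decline, an on-call social worker. It does not address being overheard.
- *Section 5.1, Safety and Data Monitoring Plan:* a general undertaking to monitor privacy, with no procedure for the call.
- *Section 5.5:* a baseline need not identified or not reported at six months counts as reduced. Read literally, this covers a skipped item as well as a No.

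**The planned sample.** Section 5.6 assumes 880 randomized and 50% participation at each follow-up survey: 880 × 0.5 = 440, then 440 × 0.5 = 220, which matches the plan. That is 220 / 3 ≈ 73 per arm.

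**Veterans exposed to the scoring problem.** Let s be the share of completers who reported the safety need at index. The documents give no value, so s is assumed.

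- s = 2%: 220 × 0.02 = 4.4
- s = 5%: 220 × 0.05 = 11

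Spread evenly, that is about 1.5 to 3.7 per arm.

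**Size of the misclassification.** Assume u = 80% of these Veterans are still unsafe at six months, g = 10% to 50% give a guarded No, and r = 30% to 50% have another need that truly resolved. None of these values is in the documents.

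- Safety items falsely resolved = 220 × s × u × g
- False reductions under the first definition = 220 × s × u × g × (1 − r)

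| s | g | r | Items falsely resolved | False reductions | Percentage points of 220 |
|---|---|---|---|---|---|
| 2% | 10% | 50% | 0.35 | 0.18 | 0.08 |
| 5% | 25% | 30% | 2.2 | 1.54 | 0.7 |
| 5% | 50% | 30% | 4.4 | 3.08 | 1.4 |
| 10% | 50% | 30% | 8.8 | 6.16 | 2.8 |

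If safety is the only baseline need then r = 0, so the item count is the ceiling. At s = 5% and g = 50% that is 4.4 / 220 = 2.0 percentage points.

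**Effect on one Veteran's score.** Take three baseline needs including safety, with one other need truly resolved and safety unresolved. The true value of the second measure is 1/3 = 33%. A guarded No gives 2/3 = 67%. Coding item 10 as missing and dropping it from numerator and denominator gives 1/2 = 50%.

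**The case against.** The strongest reply is that the statistical limb is small and inferential. A false reduction needs a Veteran who said Yes to the same question by phone at index, is still unsafe, and now guards the answer. The outcome is secondary and pooled over nine needs, and section 5.5 defines no need-specific endpoint. There is no stated reason for guarding to differ between randomized arms. If it is similar, it inflates reduction everywhere and slightly dilutes contrasts; if it differs, the direction is unknown. All of this stands.

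Some stronger readings are tempting, and the documents do not support them.

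- *That the voicemail discloses something sensitive.* It reveals participation in a study of resource needs, but no specific need, answer or safety concern. The study name already goes to homes in two arms on the Appendix P letterhead. What remains is an inconsistency: the voicemail gives the study name and the branch for another person answering does not.
- *That at least 440 Veterans will be called without completing, mostly through voicemail.* The 50% is a deliberately conservative assumption. At the prior study's 35% loss the figure is 880 × 0.35 = 308. Non-completion can also include refusals and withdrawals, and no voicemail rate is given.
- *That the script breaks the promise that "all possible measures will be taken to assure Veteran confidentiality".* That sentence sits in a paragraph about storing and handling survey data, not about calls.
- *That no safe-contact rule exists anywhere, or that the index call has the same gap.* The invitation materials and much of the Appendix G script were not in the text available, so neither can be asserted.

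A bystander to a handset call would hear only yes or no to item 10. That lessens the exposure but does not remove it, since a speaker or a nearby listener is possible and the script does not ask.

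**Conclusion.** The point holds as a participant-protection gap with a minor measurement consequence. The six-month script asks the safety question after a time check only, offers Yes and No only, and feeds a rule that scores a guarded No from a Veteran with that baseline need as a reduction.

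Under the assumed 2% to 5% prevalence, about 4 to 11 of 220 completers are exposed to the scoring problem. The false reduction in the pooled outcome runs from about 0.1 to 1.4 percentage points, or 2.8 at an assumed 10%. For the safety need taken alone the distortion could be large, because so few Veterans carry it. These figures rest on assumed values and only show scale. That Veterans will be overheard, or will answer No, is an inference from the script and not a documented fact: they may.

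The case for changing the script does not depend on prevalence. It should be made, but it does not threaten the primary outcome or the main comparison.

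**What to change.** 1. In Appendices J and K, after the time check, add: *Are you somewhere you can talk privately?* If not, use the existing branch that schedules another time. Appendix J needs it too, because its first question reads the Veteran's identified needs aloud and collects the primary outcome.
2. Repeat the check immediately before Appendix K item 10. Add a response code, *not asked – not private / declined*, recorded as missing and never as No.
3. In section 5.5, state that a need with this code is left out of both numerator and denominator of the reduction measures. If safety was the only baseline need, both measures are then missing for that Veteran. As the three-need example shows, this removes the false credit but does not recover the true value, so report use of the code by arm.
4. As a minor addition, drop the study name from the voicemail so that it matches the branch for another person answering.

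The cost is a few script lines, one REDCap code and a minor IRB amendment, with a few calls rescheduled and a few item 10 answers missing. No arm, sample size or model changes. The sponsor should also check whether the full Appendix G already has a privacy check, so that the item is asked under the same conditions at index and at six months.
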